[figure not shown]
SafeBoosC III two-year follow-up

Safeguarding the Brain of our smallest Children

Cerebral near-infrared spectroscopy monitoring versus treatment as usual for extremely preterm infants: a protocol for the follow-up study for the SafeBoosC-III trial

Sponsor:

Region Hovedstaden
Department of Neonatology 5024, Rigshospitalet
[name]
[contact]
Email: [contact]

SafeBoosC III

SAFEGUARDING THE BRAIN OF OUR SMALLEST CHILDREN

Revision history

Version	Author	Date	Major changes
1.0 draft	The SafeBoosC-III Trial Group	17.05.2021	Initial version
2.0 draft	The SafeBoosC-III Trial Group	27.05.2021	
• Condensing of exploratory outcomes• Addition of Bayley IV to the co-primary outcomes and handling of scores

Summary

Background

In the SafeBoosC-III trial, the objective is to investigate the effect of treatment based on cerebral near-infrared spectroscopy (NIRS) monitoring of brain oxygenation compared with treatment as usual in extremely preterm infants. The primary outcome of the trial is death or survival with severe brain injury at 36 weeks' postmenstrual age. Despite an association between severe brain injury diagnosed in the neonatal period and later neurodevelopmental disability, this relationship is not always strong. Therefore, if treatment based on cerebral NIRS monitoring decreases the risks of death or survival with severe brain injury, it is important to document if the beneficial effect persists into early childhood, in the form of better neurodevelopmental outcome. Furthermore, it is also important to identify evidence of unexpected harms. It would be unfortunate if cerebral NIRS monitoring became standard practice without good evidence that long-term patient-relevant benefits outweigh possible harms. In the SafeBoosC phase-II trial, 115/135 alive infants were followed-up at 24 months' corrected age to test if the intervention was beneficial in terms of improving neurodevelopment. No significant differences were found between the experimental versus control group. However, the trial was not powered to detect differences in long-term clinical outcomes. As the SafeBoosC-III trial intends to randomise 1600 infants, there is potential to achieve sufficient power for a meaningful assessment of the experimental intervention's effect on long-term neurodevelopment, as well as an evaluation of unexpected harms.

Methods

In total, 1600 infants will be randomised in the SafeBoosC-III trial. We expect approximately 1250 infants to survive and potentially be available for follow-up.

Inclusion criteria: Participation in the SafeBoosC-III trial and enrollment in a neonatal intensive care unit (NICU) taking part in the follow-up study, with parental consent according to local regulations.

Exclusion criteria: Parental objection to the use of their child's data in the follow-up study.

Participation criteria for NICUs: All NICUs participating in the SafeBoosC-III trial will be invited.

Assessments: We aim to collect follow-up data on as many children as possible by including data from routine neurodevelopmental follow-up programmes, utilizing all other health care records from the age of at least 12 months and by parental questionnaires including the PARCA-R.

Blinding: Due to the nature of the trial intervention, children and their parents will not be blinded to treatment allocation. A local co-investigator who is blinded to group allocation will conduct outcome assessments. To ensure that outcome assessment from health care records is blinded, the principal investigator and the co-investigator from each NICU will develop a local blinding procedure describing their individual workflow. Each local NICU blinding process will be approved by the central trial unit. Data managers, statisticians and those writing the abstracts as well as drawing conclusions will also be blinded.

Outcomes

There will be two co-primary outcomes:

Dichotomous effect measure: death or moderate-or-severe neurodevelopmental disability

A child will be classified with moderate-or-severe neurodevelopmental disability if any of the following conditions are present: cerebral palsy with a Gross Motor Function Classification Score ≥ 2 ; a cognitive function score below -2 standard deviations from the norm (or Bayley-III/IV < 85); hearing impairment; or vision impairment. Available data from at least 12 months' corrected age from health care records, including standardised neurodevelopmental assessments, as well as parental questionnaires completed between 18-30 months' corrected age will be used to assess mortality and neurodevelopment.

Power calculation: Based on answers from the questionnaire on systematic routine follow-up, as well as implementing parental questionnaires and informal assessments to classify neurodevelopment, we estimate the total sample size for the outcome death or moderate-or-severe NDD to 1600 children. Based on results from two randomised controlled clinical trials investigating neuroprotection in extremely preterm infants, it is estimated that the proportion of children with the outcome of death or moderate-or-severe NDD will be 50% in the control group.

An indicative power calculation shows that if we want to test a risk difference of eight percent between the experimental and control group, at an alfa of 2.5% and a sample size of 800 infants in each group, i.e. a total of 1600, we will reach a power of 80%.

Continuous effect measure: mean Bayley III/IV cognitive score

The cognitive scores from the Bayley III/IV assessment will constitute a single continuous outcome measure.

Power calculation: Based on answers to an investigator questionnaire, we expect to have access to data from Bayley III/IV assessments of 850 children. An indicative power estimation shows that if we want to test a mean difference of five points on the Bayley cognitive score, with a standard deviation of 20 (Cohens d' 0.25) between the experimental and the control group, at an alfa of 2.5%, and a sample size of 425 infants from each group i.e. a total of 850, we will reach a power of 90%.

The exploratory outcomes will be daily medication the last two months (yes/no), any other chronic illness (defined as any problem which has been diagnosed by a doctor and which 1) is expected to last more than a few months, 2) causes problems in everyday life, or 3) is a risk of early death or disability), mean head circumference, mean height and mean body weight.

All components of the co-primary outcomes will be reported for the two groups separately as well as effect estimates with confidence intervals and will be taken into consideration when interpreting the main results

Time plan

The first randomised infant in SafeBoosC III will reach two years of corrected age in September 2021, while the last follow-up assessment is expected to be completed before the end of 2024, which is an estimate of when the last infant randomised will reach two years of corrected age plus six months of reserve.

Organisation and funding

The SafeBoosC-III trial Steering Committee will be responsible for principal decisions. [name] will be the Coordinating Investigator. Local expenses must be covered by each NICU. The central expenses will be covered by the Sponsor (The Capital Region of Denmark, Copenhagen University Hospital).

1. Background and introduction

1.1 The population and condition

Worldwide, approximately 15 million infants are born preterm (below 37 weeks' gestational age) each year. Hereof, around 50,000 are born extremely preterm (below 28 weeks' gestational age) in countries where neonatal intensive care is offered routinely (1). The advances in neonatal intensive care over the past decades have resulted in a significant increase in the survival of extremely preterm infants (2-5). Currently, mortality is around 20%, but those surviving have a high risk of neonatal brain injury and subsequently long-term neurodevelopment disability (6). The risk of brain injury is especially high during the first days of life, as the infant transitions from intra- to extrauterine life. The combination of immature organs and impaired cerebral autoregulation may cause large fluctuations in cerebral blood flow (7), detectable by cerebral oximetry using near-infrared spectroscopy (NIRS). Brain injury acquired in the neonatal period may result in neurodevelopmental disability later in life. It is estimated that as many as 40% of surviving extremely preterm infants suffer from long-term neurodevelopmental disability such as cerebral palsy, cognitive and neurosensory deficits, attention deficit disorder, and major psychiatric disorder (8). These disabilities result in life-long consequences for the children and their families, such as reduced quality of life as well as increased health care and educational costs (9, 10). Evidence suggests that cerebral hypoxia is associated with the risk of brain injury as well as death in extremely preterm infants. Thus, it is plausible that a reduction of cerebral hypoxia during the first days of life may reduce the risk of severe brain injuries (11) and thus the risk of later neurodevelopmental disability (12).

1.2 The SafeBoosC consortium

1.2.1 The SafeBoosC II trial

The SafeBoosC phase-II trial demonstrated that NIRS monitoring in combination with an evidence-based treatment guideline reduced the burden of cerebral hypoxia and hyperoxia by more than 50%, compared with treatment as usual, during the first 72 hours of life (13). Furthermore, there were trends towards reduced mortality and occurrence of severe brain injury assessed at 36 weeks' postmenstrual age (PMA). In total, 115/135 (85%) infants that were alive at 24 months' corrected age were followed-up to test if the intervention was beneficial in terms of improving neurodevelopment later in life. No differences were found between the experimental and control

group in regards to the mean mental developmental index assessed by the Bayley II (89.6 ± 19.5 versus 88.4 ± 14.7 , $p=0.77$) or the total Ages and Stages Questionnaire score (215 ± 58 versus 213 ± 58 , $p=0.88$). The number of infants with moderate-or-severe neurodevelopmental disability were also similar, with ten (15%) in the experimental group and six (12%) in the control group ($p = 0.58$) (12). However, the SafeBoosC II trial was not powered to detect a relevant difference on any of the long-term clinical outcomes and thus there is a possibility that the neutral results were due to type II errors (14). Based on the above, the larger SafeBoosC-III trial is now being conducted, to test the effect of the intervention on clinical outcomes.

1.2.2 The SafeBoosC III trial

SafeBoosC III is a multi-centre, international, pragmatic phase III clinical trial investigating the effects of treatment guided by cerebral NIRS monitoring in extremely preterm infants (15). The hypothesis is that treatment based on cerebral NIRS monitoring of cerebral oxygenation in extremely preterm infants will result in a reduction of death or severe brain injury at 36 weeks' PMA. Infants randomised to the experimental group are monitored during the first 72 hours of life and receive cardio-respiratory support guided by cerebral NIRS monitoring (11). The NIRS sensor must be placed within six hours from birth. The control group does not receive any cerebral NIRS monitoring and is treated according to local guidelines and clinical practices. The SafeBoosC III trial will randomise 1600 infants, having started in June 2019 with recruitment expected to be completed by the end of 2021. Nearly 90 neonatal intensive care units (NICUs) from Europe, USA, China and India have signed up to take part in the trial (15). As of May 1st 2021, over 1000 infants have been randomised. The trial is registered at clinicaltrials.gov (NCT03770741).

The original sample size of the SafeBoosC III trial is calculated based on the primary outcome, which is a composite of death or severe brain injury at 36 weeks' PMA (16). Severe brain injury is defined as cerebral haemorrhage grade III or IV, cystic periventricular leukomalacia, cerebellar haemorrhage, post-haemorrhagic ventricular dilatation or cerebral atrophy detected on any of the cerebral ultrasound scans that are routinely performed in these infants up until 36 weeks' PMA or discharge to home, whichever comes first.

1.3 Assessment of brain injury and neurodevelopment

1.3.1 Ultrasound

Cerebral ultrasound is used to diagnose neonatal brain injury in the SafeBoosC III trial at 36 weeks' PMA. Severe (grade III or IV) periventricular-intraventricular haemorrhage is associated with an increased risk of adverse neurodevelopmental outcomes, including cerebral palsy and lower cognitive scores, but odds ratios are only 2 to 3 (18). Cystic periventricular leukomalacia is less common, but a stronger predictor of cerebral palsy and developmental delays for extremely preterm infants (19).

Cerebral ultrasound is less sensitive in the detection of mild to moderate types of brain injury as compared to magnetic resonance imaging (20, 21). This can potentially result in an underestimation of infants at risk of long-term neurodevelopmental disabilities. For example, in one study, among extremely preterm infants with no ultrasound abnormalities in the neonatal period, 23% had delayed mental development and 26% had delayed psychomotor development at two years of age (19). Thus, despite neonatal brain injury diagnosed by ultrasound being a clinically relevant outcome, it is not a definitive surrogate for long-term neurodevelopment, a more patient-relevant outcome. Therefore, assessment later in life is also important.

1.3.2 Neurodevelopmental assessment

While neuropsychological abilities can only fully be assessed in adulthood, very young childrens' abilities to walk, talk, see, hear, and develop at approximately the same pace as peers, is relevant in itself for the full life of a child, as well as being relevant milestones in the overall neurodevelopmental trajectory. Therefore, assessment in early childhood is relevant, optimally by a standardised neurodevelopmental assessment, which measures the child's skills compared to a norm. Assessment at two years of corrected age is commonly used clinically as well as for research purposes (22). The predictive value of such assessments for later function is relatively poor for the individual child, except for the most severe disabilities with score values below minus 3 SD (23, 24). This is likely partly due to the difficulties of assessing young, intermittently cooperating children, but also due to the irregular pace of development in individual infants, as well as the fact that some elements of cognition only develop later, and that childhood and upbringing also influence development. As an example, while measures of intelligence quotient (IQ) track well from the age of five years and onwards through adult life, measures of cognition at two years do not correlate well with measures of IQ at 5 years (8). However, on a group level, these assessments fairly consistently quantify differences between extremely preterm born children and children born

at term (nearly one SD). Therefore, these assessments are likely to be valuable as outcome measures in randomised clinical trials, since assessments will be compared on a group level (25).

Multiple validated methods exist to assess neurodevelopment in early childhood, with the most frequently used being the Bayley Scales of Infant Development (Bayley) and the Griffiths Scale of Childhood Development (Griffiths) (32,33). However, these assessments are lengthy for both the children, parents and clinicians and reliability is compromised if a child is unable to cooperate well. Parental questionnaires, drawing on the knowledge of the child's abilities in daily life, may be a good, pragmatic and cost-effective substitute for a face-to-face neurodevelopmental assessment by a qualified examiner (26). The Parent Report of Children's Abilities-Revised (PARCA-R) is a parental questionnaire, evaluating cognitive and language development at two years of age (27). It has high sensitivity and specificity for identifying neurodevelopmental disability among very preterm infants, supporting its use as an outcome measure in randomised trials (28, 29). For further elaboration please see section 2.6 'Outcome assessment tools' in the Methods section.

1.4 Potential harms

It would be unfortunate if cerebral NIRS monitoring became standard practice without good evidence that patient-relevant benefits outweigh harms. As an example, studies investigating the use of early systemic postnatal corticosteroids for preventing bronchopulmonary dysplasia (BPD) (30) in preterm infants, at first showed significantly improved short-term outcomes, such as earlier extubation and less prevalence of BPD. However, when two-year follow-up assessments were conducted, several adverse neurological effects were reported, in particular cerebral palsy (31). Based on this, the clinical use of corticosteroids was restricted to those infants at very high risk of BPD or death. Studies like these demonstrate the importance of long-term follow-up for randomised clinical trials.

The SafeBoosC-II trial did indeed show a trend towards higher prevalence of BPD and retinopathy of prematurity in the experimental group. Therefore, it is possible that cerebral NIRS monitoring may cause harm. Such harms could theoretically be caused by inappropriate modifications in cardio-respiratory support based on hypoxic values and/or unnecessary infant disturbance.

1.5 Recruitment and loss to follow-up

Loss to follow-up in studies with long-term outcomes is common and data are rarely missing completely at random. Studies have shown that children lost to follow-up often have a lower socioeconomic status and tend to have more neurodevelopmental impairment than children participating in follow-up programmes (41). Factors affecting loss to follow-up include maternal education, age, substance abuse, poverty level, and marital status, among others (42). As this is a pragmatic study, we do not expect that all eligible children will participate. However, we aim to ascertain follow-up data on as many children as possible by collecting data from all health care records from 12 months' corrected age onward as well as by parental questionnaires (see Methods section 2.6 'outcome assessment tools').

In the Summer of 2020, when recruitment was well-established, a questionnaire was sent out to all active NICUs asking if they were interested in participating in the follow-up study and how their local follow-up programmes were structured. Sixty-two NICUs completed the questionnaire and all expressed interest in taking part in the two-year follow-up study. All NICUs reported having a systematic follow-up programme of extremely preterm infants. Eighty percent reported a routine follow-up rate of 75% or more, and 65% routinely perform a Bayley III/IV assessment between 18 and 30 months' corrected age. Furthermore, several other standardised developmental assessments and screening methods were reported to be utilized from 18 to 30 months' corrected age, including Griffiths, Denver Developmental Screening Test II, Peabody II, Gessell, Ages and Stages Questionnaire, PARCA-R, Alberta Infant Motor Scales, etc. Almost all NICUs conduct a standardised neurodevelopmental assessment around two years' corrected age. Based on these investigator questionnaire responses, we have planned the SafeBoosC-III two-year follow-up study.

Since the summer of 2020, more NICUs have joined the SafeBoosC-III consortium, thus strengthening the chances of obtaining sufficient statistical power for a meaningful test of the intervention's effect on neurodevelopment.

2 Methods

2.1 Objective and hypothesis

The objective of the SafeBoosC III follow-up study is to investigate the benefits and harms of treatment guided by cerebral NIRS monitoring of brain oxygenation in extremely preterm infants during the first 72 hours of life, assessed at two years' corrected age.

The hypothesis is that the intervention will decrease a composite of death or moderate-or-severe neurodevelopmental disability at two years' corrected age, and/or increase cognitive function in survivors assessed by the Bayley III/IV test, with insignificant harms.

2.2 Inclusion criteria

Participation in the SafeBoosC III trial, enrollment in a NICU taking part in the follow-up study, and parental consent according to local regulations.

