2.3 Exclusion criteria

Parental objection to use of their child's data in the study.

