2.9 Participation criteria

All NICUs participating in the SafeBoosC-III trial will be invited to participate in the follow-up study. In the spring of 2021, NICUs will receive an official invitation to participate, along with this protocol, which has been approved by the Steering Committee. NICUs will be asked to state explicitly what data they will provide in the follow-up and as well as their expected follow-up percentage. NICUs will be encouraged to provide as much data as possible since this will strengthen the quality of the study.

The tasks for NICUs are as follows:

1. Obtain addendum ethical approval to conduct the follow-up study in their NICU, if necessary.

2. Obtain addendum contract and legal approval, if necessary
3. Delegate the review of health care records and outcome assessment to a co-investigator, who can be blinded to the group allocation in the SafeBoosC-III trial.
4. Develop local work flow and blinding procedure
5. Ensure that the contact information, ideally e-mail addresses of the parents, is maintained and that links to the web-based platform with the PARCA-R questionnaire and the health and development questionnaire are forwarded to the parents as necessary

Parents of all infants included in the SafeBoosC III trial, and alive at the time point where routine follow-up assessments are initiated, should be invited to participate in the follow-up study.

Since the first randomised infant in SafeBoosC III will reach two years of corrected age in September 2021, we expect that follow-up assessments will begin around this time point. The last follow-up assessment is expected to be completed before the end of 2024 since this is the time where we expect the last randomised infant to reach two years of corrected age plus six months of reserve.

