2.10.2 Consent

When infants were randomised in the SafeBoosC-III trial, the parents were made aware of the possibility of a potential follow-up study and permission to contact families as foreseen in the information sheet the parents were given at inclusion. The study-related interventions consist of extracting data from health care records, and parental questionnaires. The need for explicit consent for using clinical data from health care records for the SafeBoosC-III follow-up study may differ

between countries. In some countries, turning up for examination or answering questionnaires will be considered sufficient, implicit consent.

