3.1 Primary analyses

The primary analysis of all outcomes will be based on the intention-to-treat population. Mixed-effect linear regression and mixed-effect logistic regression will be used to analyse the dichotomous and continuous co-primary outcomes, respectively. Data from all participating sites will be used in the primary analysis of both co-primary outcomes. In the regression models, 'site' will be included as a random effect, while 'gestational age below or above 26 weeks of postmenstrual age' and 'group allocation' will be included as fixed effects. To correct for multiple testing, the threshold for statistical significance will undergo Bonferroni adjustment, and thus a p-value of 0.025 for each primary outcome is chosen. Superiority of the intervention will only be claimed if at least one of the two co-primary outcomes is statistically significant. All other outcome results will be considered hypothesis-generating only. In addition, we will perform a range of pre-defined sensitivity analyses to inform the interpretation of the results of the primary analysis. A full statistical analysis plan will be developed and submitted for publication before the analysis of the SafeBoosC-III trial data.

[figure not shown]

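### The consent, exclusion and data-source rules do not deliver the all-randomised population on which the death-or-disability co-primary is sized

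*Combined protocol and SAP*

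**What the plan says.** **Who enters.** Section 2.2 lists the inclusion criteria as "Participation in the SafeBoosC III trial, enrollment in a NICU taking part in the follow-up study, and parental consent according to local regulations". Section 2.3 has one exclusion: "Parental objection to use of their child's data in the study". Section 2.9 directs the invitation to parents of trial infants "alive at the time point where routine follow-up assessments are initiated, should be invited to participate in the follow-up study". Section 2.10.2 says that the need for explicit consent varies between countries and adds: "In some countries, turning up for examination or answering questionnaires will be considered sufficient, implicit consent". Section 2.8 states that parents are not blinded to allocation.

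**Where the outcome comes from.** The Summary, under Outcomes, names "Available data from at least 12 months' corrected age from health care records, including standardised neurodevelopmental assessments", together with parental questionnaires, as the material for judging both mortality and neurodevelopment. Section 2.4.2 sets a floor of 12 months' corrected age for assessing all outcomes from records. Section 2.7 bases the composite mainly on records from 18 to 30 months, then on questionnaires, then on an informal judgement from 12 months onward. Appendix A classifies children as NDD, no NDD or unclassifiable and has no rule for death.

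**Who is to be analysed.** Section 3 expects 1264 of 1600 infants to be alive at two years but sizes the composite on all 1600, 800 per group. Section 3.1 says: "The primary analysis of all outcomes will be based on the intention-to-treat population".

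**The concern.** The eligibility rules turn on events after randomisation: survival to the invitation, and the parents' response to it. The analysis plan assumes that neither matters. Two distortions follow, in opposite directions.

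- **Deaths may be left out.** Parents of an infant who died are not invited to give follow-up consent. Where local rules require that consent explicitly, nothing says how the infant meets section 2.2. Whether a death counts could then depend on national consent rules. The estimand would shift towards disability among survivors.
- **Decliners are removed.** Objection is an exclusion, so a randomised, living child leaves the study on the decision of parents who know the allocation. Section 1.5 itself says that follow-up data are rarely missing completely at random. If deaths are all counted while decliners are dropped, deaths carry too much weight in the analysed set.

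**Working it through.** **Inputs (section 3, power estimations).** 1600 infants, 800 per group; mortality 21%, tentative, from the first 580 infants, taken here as both groups combined; control composite 50%; planned difference 8 points, hence 42% in the experimental group; alpha 2.5%, assumed two-sided. The documents give neither mortality by group nor any share of deaths that might be left out. Both are assumptions below.

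**1. The plan's own figure.** 1600 × (1 − 0.21) = 1264 survivors, as stated, which leaves 336 deaths. Since 1264 + 336 = 1600, the stated sample size is reached only if every death is counted.

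**2. Weight of deaths in the composite.**
- Control group, if its mortality is 21%: 800 × 0.21 = 168 deaths; 800 × 0.50 = 400 events; 168/400 = 42.0%.
- Both groups, at 21% overall: events 800 × 0.50 + 800 × 0.42 = 400 + 336 = 736; deaths 336; 336/736 = 45.7%.

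**3. Effect of leaving deaths out.** With composite proportion p, mortality m and a share f of deaths left out, the observed proportion is (p − f·m)/(1 − f·m). Three splits, each averaging 21%, put none, half or all of the 8-point benefit on mortality. With no deaths lost (f = 0), all three give 50% vs 42% and power of 83.4%. The plan states 80%, which is slightly conservative; nothing here depends on that gap.

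| Mortality, control / experimental (assumed) | Deaths left out (assumed) | Observed control vs experimental | Difference | Power |
|---|---|---|---|---|
| 21% / 21% | half | 44.1% vs 35.2% | 8.9 points | 88.9% |
| 21% / 21% | all | 36.7% vs 26.6% | 10.1 points | 94.9% |
| 23% / 19% | half | 43.5% vs 35.9% | 7.6 points | 75.7% |
| 23% / 19% | all | 35.1% vs 28.4% | 6.7 points | 62.1% |
| 25% / 17% | half | 42.9% vs 36.6% | 6.2 points | 56.9% |
| 25% / 17% | all | 33.3% vs 30.1% | 3.2 points | 15.5% |

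Example, 25% / 17% with all deaths lost: control (0.50 − 0.25)/0.75 = 33.3%; experimental (0.42 − 0.17)/0.83 = 30.1%.

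**4. Effect of dropping decliners while counting all deaths.** As an illustration only, suppose 25% of control survivors are dropped, unrelated to NDD. (Section 1.5 reports that 80% of responding NICUs follow up 75% or more; the share of parents who would object is not given.) Survivors 632 × 0.75 = 474; analysed 474 + 168 = 642. Deaths become 168/642 = 26.2% of the group instead of 21%. NDD cases are (400 − 168) × 0.75 = 174, so the composite is (168 + 174)/642 = 53.3% instead of 50%.

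**The case against.** The strongest reply is that the documents plainly mean deaths to count. The sample size of 1600 is impossible without them. Section 2.1 reserves the phrase about survivors for the cognitive outcome. Death is not an exclusion. Section 2.9 concerns NICU tasks and invitations, and inviting only parents of living children to assessments is natural. All of this stands.

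It also rules out some stronger readings that a reader might infer:

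- **That infants who died cannot be included where consent is implied by attendance.** Section 2.10.2 calls attendance sufficient, not necessary. Local rules may require no new consent, and parents were told of a possible follow-up when their infant was randomised.
- **That a death between 36 weeks' postmenstrual age and 12 months' corrected age falls outside both data sources.** The 12-month floor can be read as fixing when the assessor looks. An assessor at that point can see that a child has died, and a site must know who is alive in order to invite. The route is unstated, not closed.
- **That losing deaths must dilute the effect or cost power.** Step 3 shows that it can do the opposite.

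Section 3 also defers analysis details to a separate plan. That does not dispose of the point. Consent criteria, exclusions and data-entry content are protocol rules on which NICUs act before any analysis, and a later analysis plan cannot recover infants or fields never collected. The intention that deaths count is what shows the mismatch with sections 2.2, 2.3, 2.4.2 and 2.7.

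**Conclusion.** The point holds as a mismatch between stated rules, not as proof that deaths are excluded. The size and analysis of the composite require every randomised infant; the consent criterion, the exclusion for objection and the 12-month data floor do not supply them.

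Much of the outcome is exposed: about 42% of control-group events if control mortality is 21%, or about 46% of all events at 21% overall. The effect on the treatment comparison is not fixed in direction. If all deaths were left out, the 8-point difference would become 3.2 points with the benefit wholly on mortality and 10.1 points with equal mortality. These figures rest on the tentative 21%, the planned 50% vs 42%, and assumed splits and losses. Loss of all deaths is an outer bound, because consent rules differ by country.

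Two problems do not depend on those assumptions: what the composite measures could vary by country, and exclusion on objection allows selection after randomisation by parents who know the allocation.

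**What to change.** Amend sections 2.2, 2.3 and 3.1 as follows.

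- Define the population for death or moderate-or-severe NDD as every infant randomised in a participating NICU.
- Count death from any cause from randomisation to two years' corrected age, from SafeBoosC-III data and NICU records where local law allows.
- Apply follow-up consent only to the collection of follow-up data on survivors.
- Treat a survivor whose parents decline as randomised with a missing outcome, not as excluded. Report these children by group and handle them in the missing-data analysis. Relabelling alone would leave the over-weighting in step 4 in any complete-case result.

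Sections 2.4.2 and 2.7 and Appendix A should say that the 12-month floor applies to neurodevelopmental evidence, not to death.

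The cost is wording, one extra e-CRF field for later deaths, and more visible missing data. The plan must also list the countries whose law bars use of data on deceased infants, and record objections from bereaved parents.
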